16. SAFETY REPORTING AND DEFINITIONS

Safety assessments will consist of monitoring and recording any adverse events reported, including serious adverse events and non-serious adverse events; measurement of protocol-specified safety laboratory assessments; measurement of protocol-specified vital signs; and other protocol-specified tests that are deemed critical to the safety evaluation of the study.

16.1. Adverse Events Monitoring

All AEs regardless of seriousness or relationship to IMP, spanning from the signature of the informed consent form, until the end of the study as defined by the protocol for that patient, are to be recorded on the corresponding page(s) included in the CRF and reported as described in the following sections.

For all adverse events, the investigator must pursue and obtain information adequate both to determine the outcome of the adverse event and to assess whether it meets the criteria for classification as a serious adverse event requiring immediate notification to Sponsor or its designated representative.

For all adverse events, sufficient information should be obtained by the investigator to determine the causality of the adverse event. The investigator is required to assess causality. For adverse events with a causal relationship to the investigational product, follow-up by the investigator is required until the event or its sequelae resolve or stabilize at a level acceptable to the investigator, and Sponsor concurs with that assessment. This may imply that observations will continue beyond the last planned visit per protocol, and that additional investigations may be requested by the Monitoring Team up to as noticed by the sponsor

Whenever possible, diagnosis or single syndrome should be reported instead of symptoms. The Investigator should specify the date of onset, intensity, action taken with respect to IMP, corrective treatment/therapy given, additional investigations performed, outcome and his/her opinion as to whether there is a reasonable possibility that the AE was caused by the IMP.

16.2. Reporting Period

For serious adverse events, the reporting period to Sponsor or its designated representative begins from the time that the subject provides informed consent, which is obtained prior to the subject's participation in the study, i.e. prior to undergoing any study-related procedure and/or receiving investigational product, through and till the end of the Follow Up Period as specified in the study protocol.

Any serious adverse event occurring any time after the reporting period must be promptly reported if a causal relationship to investigational product is SUSPECTED.

16.3. Adverse Event (AE):

An adverse event is any untoward medical occurrence in a clinical investigation subject administered a product or medical device; the event need not necessarily have a causal relationship with the treatment or usage.

Examples of adverse events include but are not limited to:

- Abnormal test findings
- Clinically significant symptoms and signs
- Changes in physical examination findings
- Hypersensitivity
- Progression/worsening of underlying disease

Additionally, they may include the signs or symptoms resulting from:

- Drug overdose
- Drug withdrawal
- Drug abuse
- Drug misuse
- Drug interactions
- Drug dependency
- Extravasation

Exposure during pregnancy
Drug Quality Defect that has impact on the patient safety

16.4. Serious Adverse Events

A serious adverse event or serious adverse drug reaction is any untoward medical occurrence at any dose that:

Results in death
life-threatening Event (Immediate Risk Of Death)
Requires inpatient hospitalization or prolongation of existing hospitalization
Results in persistent or significant disability/incapacity
Results in congenital anomaly/birth defect
Important medical event

Medical and scientific judgment should be exercised in determining whether an event is an important medical event. An important medical event may not be immediately life-threatening and/or result in death or hospitalization. However, if it is determined that the event may jeopardize the subject and/or may require intervention to prevent one of the other adverse event outcomes, the important medical event should be reported as serious

16.4.1. Instructions for Reporting Serious Adverse Events

In the case of occurrence of a SAE, the Investigator must immediately:

1. Sending within 24 hours, preferably by e-mail the signed and dated corresponding page(s) from the CRF to the representative of the Monitoring Team whose name, fax number and e-mail address appear on the Clinical Trial Protocol and qualified person for pharmacovigilance
2. ATTACH the photocopy of all examinations carried out and the dates on which these examinations were performed. Care should be taken to ensure that the patient's identity is protected and the patient's identifiers in the Clinical Trial are properly mentioned on any copy of source document provided to the Sponsor. For laboratory results, include the laboratory normal ranges;
3. All further documentation should be sent to the Monitoring Team within 1 working day of knowledge. In addition, any effort should be made to further document each SAE that is fatal or life threatening within the week (7 days) following initial notification

17. STATISTICAL METHODOLOGY

17.1. Determination of Sample Size

Sample size: Records for 100 patients who underwent major orthopedic surgery collected from 1 site

The sample size is based on literature review for previous studies, and a sample of 168 patients will be sufficient to detect an incidence of 12.5% of DVT with an acceptable error of 5%, and a 95% confidence level

17.2. Analysis Variables:

17.2.1. Primary analysis variables:

Proportion of patients experienced new onset symptomatic thrombosis
The number of clinical PE (Pulmonary Embolism) events will be measured by spiral CT

17.2.2. Secondary analysis variables:

Number of adverse events recorded
Proportion of patients experienced major bleeding

17.2.3. Statistical Method:

Descriptive analysis:

All statistical tests used a significance level of $P=0.05$, two tailed tests were performed for all analyses used statistical testing.

Descriptive analysis for quantitative data will include count, mean with 95% CI, standard deviation, median, minimum and maximum. For qualitative categorical variables; frequency and percentage and 95% confidence interval will be applied.

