Title Page

A Prospective, Single- Center, Phase IV Interventional, Single Arm **T**rial for the
Evaluation of subcutaneous recombinant **H**irudin 15 mg (RB variant) in
prophylaxis of Deep Vein Thrombosis (**DVT**) post major orthopedic operations

Principle Investigator: [name]

Sub Investigator: [name]

Study Site: Alexandria University

Protocol Name: THRIVE-DVT

Protocol Number: Sub-Thromb-001

Version:1.0, amendment 1

Date: 25th of January, 2022

CONFIDENTIALITY STATEMENT

This study was performed in compliance with Good Clinical Practice (GCP), including the archiving of essential documents. This report has been prepared in accordance with ICH Harmonized Tripartite Guideline on the Structure and Content of Clinical Study Reports, dated November 1995.

Any and all information presented in this document shall be treated as confidential and shall remain the exclusive property of **Minapharm Pharmaceuticals** (or any of its affiliated companies). The use of such confidential information must be restricted to the recipients for the agreed purpose and must be disclosed, published or otherwise communicated to any unauthorized persons, for any reasons, in any form whatsoever without the prior written consent of **Minapharm Pharmaceuticals** (or the concerned affiliate company); "Affiliate Company" means any corporation, partnership or other entity which at the date of communication or afterwards with **Minapharm Pharmaceuticals**

1. Synopsis

Title	Description
Study Title	Prospective, Single- Center, Interventional, Single Arm Trial for the Evaluation of subcutaneous recombinant Hirudin 15 mg (RB variant) in prophylaxis of Deep Vein Thrombosis (DVT) post major orthopedic operations
Study number	Sub-Thromb-001
Study Phase	Phase IV
Study Design	Prospective, Single arm, single-center
Study population	Patients undergoing major orthopedic operations
Study procedures	
Drug: r-Hirudin Other Name: Thrombexx
 
100 Patients will be treated with r-Hirudin (Thrombexx) for a total of 15 days beginning with 15 mg BID s.c starting 6 hours after surgery or upon adequate hemostasis and continued until end of study.

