4. INTRODUCTION

4.1. Background

Hirudin is the most potent naturally-occurring direct thrombin inhibitor (DTI), and the first parenteral anticoagulant used on humans.¹

Originally derived from the medicinal leech (*Hirudo medicinalis*), it consists of a 65 amino acids polypeptide chain, forming non-covalent, equimolar, non-reversible 1:1 complexes with α thrombin.¹ When hirudin-bound, thrombin-catalyzed reactions and fibrinogen clotting are blocked, and coagulation is subsequently inhibited.² Hirudin was previously produced in limited amounts, however, recombinant DNA technology allowed its mass production.³ These recombinant forms bind bivalent to thrombin with pharmacokinetic and anticoagulant profile similar to that of the native form.⁴

Recombinant Hirudin is a direct inhibitor of thrombin. It binds in 1:1 ratio with thrombin thus blocking the coagulation cascade and the formation of thrombi.⁵

Unlike heparins, the action of Hirudin is totally independent from any coagulation cofactor that may interfere or alter its action.⁵

Thrombexx is useful in the prevention of thromboembolic complications in at risk patients thrombexx (15 mg) is administered by subcutaneous injection 5-15 minutes before orthopedic or general surgery (after induction of regional block anesthesia) then 15 mg twice daily for 9-12 days and in bedridden patients until patient is fully ambulant (maximum 12 days)⁵

According to the FDA Therapeutic Equivalence Evaluation, 30th Edition, the biosimilar of recombinant hirudin, Desirudin is FDA approved, therefore, the same applies to recombinant hirudin in Egypt.

4.2. Correlative studies:

- 1- Study of Prevention of Thromboembolic with Use of Recombinant Hirudin, Results of a Double-Blind, Multicenter Trial Comparing the Efficacy of Desirudin (Revasc) with That of Unfractionated Heparin in Patients Having a Total Hip Replacement⁶ which showed that desirudin to be more effective than heparin in the prevention of deep vein thrombosis, without any increase in the requirements for transfusion or the risk of hemorrhage. The prevalences of over-all and proximal deep-vein thrombosis in the 174 patients who had been managed with desirudin and were included in the per-protocol analysis were 7 and 3 per cent (thirteen and six patients), respectively.⁶

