The sample size is based on literature review for previous studies, and a sample of 168 patients will be sufficient to detect an incidence of 12.5% of DVT with an acceptable error of 5%, and a 95% confidence level

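### The stated precision (±5 points at 12.5% DVT, 95% confidence) needs 168 patients, but the trial takes 100, which gives ±6.5 points

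*Protocol*

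**What the plan says.** Protocol 17.1 (Determination of Sample Size) opens with the planned number: "Records for 100 patients who underwent major orthopedic surgery collected from 1 site". It then says the size rests on a literature review and that "a sample of 168 patients will be sufficient to detect an incidence of 12.5% of DVT with an acceptable error of 5" per cent, with 95% confidence. SAP 8.1 repeats both statements, including "a sample of 168 patients will be sufficient to detect an incidence of 12.5% of DVT".

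Everywhere else the number is 100. The protocol synopsis says "100 Patients will be treated with r-Hirudin (Thrombexx) for a total of 15 days" and lists 100 as the sample size. The SAP table shells that show a denominator (Tables 1 to 7, 12, 13, 20 and 21) are headed N = 100. The figure 168 occurs only in the justification, and nothing explains the step down to 100.

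The planned analysis of proportions is a frequency, a percentage and a 95% confidence interval, by a method not named (protocol 17.2.3, SAP 8.2.3). There is no comparator, success threshold, powered hypothesis or interim analysis.

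**The concern.** One section gives two sample sizes, and the only reasoning offered supports the one that is not used. Either the 168 calculation is meant to justify 100, in which case it fails, or 100 has no justification at all.

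In a single-arm trial reported by confidence intervals, the width of the interval is what the sample size buys, and it is the only planning property these documents state. A study report that relied on 17.1 to say the trial was sized for ±5 points at 95% confidence would be wrong at the incidence the plan assumes. An ethics committee reading the section also cannot tell whether the enrolment target is 100 or 168.

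Two further weaknesses sit in the same sentence:

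- The 12.5% is tied to no named study. The hip-replacement trial described in protocol 4.2 reports overall and proximal DVT rates that, among patients "included in the per-protocol analysis were 7 and 3 per cent (thirteen and six patients"), are well below it.
- The calculation is for DVT incidence, while the primary analysis variable in protocol 17.2.1 and SAP 8.2.1 is the proportion with new symptomatic thrombosis.

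**Working it through.** **Inputs.** From protocol 17.1 and SAP 8.1: incidence p = 0.125, acceptable error d = 0.05, 95% confidence (two-sided, z = 1.95996), planned n = 100. From protocol 4.2: 7% overall DVT, which is 13 of 174 patients (7.47%).

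**1. Reproduce the plan's figure.** For the normal-approximation (Wald) interval, n = z² p(1 − p) / d².

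n = 3.8415 × 0.125 × 0.875 / 0.0025 = 168.06

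This is the plan's 168 (169 if rounded up). The match also shows that the 5% error means ±5 absolute percentage points.

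**2. Test whether another reading gives 100.** With the same inputs:

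| Method | n required |
|---|---|
| Wald, two-sided | 168.06 |
| Wald, one-sided | 118.4 |
| Wilson | 170 |
| Clopper-Pearson | 187 |
| Wald with continuity correction | 188 |

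None gives 100. A finite-population correction would do so only for a source population of about 247, and the documents state no such population.

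**3. Precision at n = 100 and 12.5%.**

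- Half-width = 1.95996 × √(0.125 × 0.875 / 100) = 1.95996 × 0.03307 = 0.0648, or ±6.48 points (about 6.0% to 19.0%).
- Ratio to the stated error: 6.48 / 5 = 1.296, about 30% wider.
- Confidence at which ±5 points holds: 0.05 / 0.03307 = 1.512 standard errors, and 2Φ(1.512) − 1 = 86.9%.

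**4. Exact (Clopper-Pearson) 95% intervals near that rate.**

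| Events / n | 95% CI |
|---|---|
| 12/100 | 6.4% to 20.0% |
| 13/100 | 7.1% to 21.2% |
| 21/168 (12.5%) | 7.9% to 18.5% |

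**5. What 100 patients would support.**

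- At p = 0.07: n = 3.8415 × 0.07 × 0.93 / 0.0025 = 100.03, so the Wald half-width at 100 is ±5.00 points.
- At the unrounded p = 13/174: n = 106.2, and the half-width at 100 is ±5.15 points.
- With no events in 100 patients, the upper limit of the two-sided 95% Clopper-Pearson interval is 1 − 0.025^(1/100) = 3.6%.

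**The case against.** The strongest reply is that the documents attach ±5 points to 168 and never say that 100 patients achieve it. That is literally so. But the sentence is the only basis given under the heading on determining sample size, so reading it as unrelated to 100 leaves 100 with no basis. Either way the text needs correction.

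A second reply is that little depends on it. The trial is descriptive, no decision rule changes, and DVT incidence is not itself a listed primary analysis variable. If symptomatic events are rarer than 12.5%, 100 patients give a narrower interval: ±3.3 points at 3% by the same formula. This limits the practical harm. It does not make the stated justification true, and it shows that the calculation was done for the wrong quantity.

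A third reply is that 100 does give ±5 points at 7%, the rate quoted from the hip-replacement trial. That may be where the number came from, but the documents do not say so; they assume 12.5%. The 7% is also a rounded, per-protocol rate from hip replacement, while this trial enrols knee arthroplasty as well.

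Two cautions on the wording of any replacement do stand. The interval method should be named, because exact limits are wider than Wald limits: 7/100 gives 2.9% to 13.9%, a half-width of 5.5 points. And the figures assume that all 100 patients are evaluable, although the plan makes no allowance for dropout.

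**Conclusion.** The concern holds. The plan's own inputs require 168 patients (169 with strict rounding) and the trial takes 100. At the assumed 12.5% incidence the 95% half-width is ±6.5 points rather than ±5, about 30% wider; equivalently, ±5 points is held with about 87% confidence. This rests on reading the 5% error as an absolute half-width, which the reproduction of 168 confirms, and on all 100 patients contributing data. The contradiction is in the current text of both documents. It must be corrected, because it is the sole stated basis for the sample size. The defect lies in the justification: 100 can stand as a number if its real precision is stated.

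**What to change.** Keep 100 patients, the number used throughout, and delete the 168 sentence from protocol 17.1 and SAP 8.1. Replace it in both places with text such as:

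> With 100 evaluable patients, the 95% confidence interval (normal approximation) has a half-width of about ±6.5 percentage points if DVT incidence is 12.5%, and about ±5.0 points if it is 7%, as in the cited hip-replacement trial. For the symptomatic-thrombosis endpoint, 0 events in 100 patients gives an exact (Clopper-Pearson) 95% upper limit of 3.6%.

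If the 12.5% is kept, its source should be cited. The cost is one paragraph in each document, no extra patients, and a stated precision that is somewhat less favourable.

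If the sponsor does want ±5 points at 12.5%, the alternative is to enrol 168 to 169 patients. That is 68 to 69 more than planned, before any dropout allowance, with matching changes to the synopsis and the SAP table shells. Leaving both numbers in place is not an option.

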17.2.4. Interim Analysis

Not applicable in this Prospective study

18. ETHICS

18.1. INDEPENDENT ETHICS COMMITTEE (IEC) OR INSTITUTIONAL REVIEW BOARD (IRB)

The protocol and the proposed informed consent form must be reviewed and approved by a properly constituted Institutional Review Board/Independent Ethics Committee (IRB/IEC) before study start. A signed and dated statement that the protocol and informed consent have been approved by the IRB/IEC must be given to Minapharm Pharmaceuticals before study initiation. Prior to study start, the investigator is required to sign a protocol signature page confirming his/her agreement to conduct the study in accordance with these documents and all of the instructions and procedures found in this protocol and to give access to all relevant data and records to Minapharm monitors and auditors and regulatory authorities as required

18.2. Ethical principles:

This Clinical Trial will be conducted in accordance with the principles laid down by the 18th World Medical Association (Helsinki, 1964) and all applicable amendments laid down by the World Medical Association and ICH guidelines for Good Clinical Practice [(E6)R1]

18.3. Laws and regulations:

This Clinical Trial will be conducted in compliance with all international laws and regulations, and national laws and regulations of Egypt in which the Clinical Trial is performed, as well as any applicable guidelines.

18.4. PATIENT INFORMATION AND CONSENT

The Investigator (according to applicable regulatory requirements), or a person designated by the Investigator, and under the Investigator's responsibility, should fully inform the Patient of all pertinent aspects of the Clinical Trial including the written information giving approval/favourable opinion by the Ethics Committee (IRB/IEC). All participants should be informed to the fullest extent possible about the study, in language and terms they are able to understand.

Prior to a patient's participation in the Clinical Trial, the written Informed Consent Form and any other local applicable documents in accordance with Egyptian laws and regulations, should be signed, name filled in and personally dated by the patient or by the patient's legally acceptable representative, and by the person who conducted the informed consent discussion. A copy of the signed and dated written Informed Consent Form will be provided to the patient.

The Informed Consent Form used by the Investigator for obtaining the patient's informed consent must be reviewed and approved by the Sponsor prior to submission to the appropriate Ethics Committee (IRB/IEC) for approval/favorable opinion.

Minapharm Pharmaceuticals will provide investigators in a separate document with a proposed informed consent form (ICF) that is considered appropriate for this study and complies with the ICH GCP guideline and regulatory requirements. Any changes to this ICF suggested by the investigator must be agreed to by Minapharm before submission to the IRB/IEC and a copy of the approved version must be provided to the Minapharm manager after IRB/IEC approval.

18.5. DISCONTINUATION OF THE STUDY

Minapharm reserves the right to discontinue this study under the conditions specified in the clinical study agreement.

18.5.1. PREMATURE DISCONTINUATION OF STUDY

Minapharm may prematurely terminate the trial if any of the following situations occurs:

APTT value for the subject increases by 2-2.5 folds

Comprehensive deficiency in the recorded data or protocol compliance so that the results of the study cannot be reliably assessed.

Occurrence of AEs necessitating termination.

Minapharm terminates the development plan for the compound.

The IRB/IEC changes its opinion regarding the safety/efficacy/relevance of the compound.

Regulatory authority decision.

If the trial is prematurely terminated or suspended for any reason, the investigators and subsequently the trial subjects will be informed promptly, standard therapy and follow-up for subjects will be assured and, where required by the applicable regulatory requirement(s), the relevant regulatory authority(s) will be informed. The IRB/IEC and all trials sites will be informed promptly and provided with a detailed written explanation for the termination or suspension. As directed by Minapharm, all study materials must be collected and all CRFs completed to the greatest extent possible.

18.6. PUBLICATION OF STUDY PROTOCOL AND RESULTS

Minapharm assures that the key design elements of this protocol will be posted in a publicly accessible database such as clinicalstudies.gov. In addition, upon study completion and finalization of the study report the results of this study will be either submitted for publication and/or posted in a publicly accessible database of clinical study results.

18.7. STUDY DOCUMENTATION, RECORD KEEPING AND RETENTION OF DOCUMENTS

Records and documents pertaining to the conduct of this study, including CRFs, laboratory test results, and medication inventory records, must be retained by the Principal Investigator for at least 15 years after completion or discontinuation of the study, or for the length of time required by local health authorities, whichever is longer. After that period of time, the documents may be destroyed.

No records may be disposed of without the written approval of Minapharm. A written notification should be provided to Minapharm prior to transferring any records to another party or moving them to another location.

